7. ADVERSE EVENTS (AE) AND SERIOUS ADVERSE EVENTS (SAE)

The investigator is responsible for the detection and documentation of events meeting the criteria and definition of an AE or SAE. During the study, in case of a safety evaluation, the investigator or site staff will be responsible for reporting AEs and SAEs, as detailed in this section of the protocol.

During the screening period, only adverse event related to the screening procedures will be collected.

Any disease progression will be reported in the eCRF both as an adverse event and documented in the efficacy section.

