Rare: Pericarditis, pericardial effusion, pericardial tamponade.

Vascular disorders

Rare: Hypotension, thromboembolic events.

Respiratory, thoracic and mediastinal disorders

Common: Pneumonia, interstitial alveolitis/pneumonitis often associated with eosinophilia. Symptoms indicating potentially severe lung injury (interstitial pneumonitis) are: dry, not productive cough, short of breath and fever.

Rare: Pulmonary fibrosis, *Pneumocystis carinii* pneumonia, shortness of breath and bronchial asthma, pleural effusion.

Not known: Epistaxis, pulmonary alveolar haemorrhage.

Gastrointestinal disorders

Very common: Stomatitis, dyspepsia, nausea, loss of appetite, abdominal pain.

Common: Oral ulcers, diarrhoea.

Uncommon: Gastrointestinal ulcers and bleeding, enteritis, vomiting, pancreatitis.

Rare: Gingivitis.

Very rare: Haematemesis, haematorrhea, toxic megacolon.

Hepatobiliary disorders (see section 4.4)

Very common: Abnormal liver function tests (increased ALAT, ASAT, alkaline phosphatase and bilirubin).

Uncommon: Cirrhosis, fibrosis and fatty degeneration of the liver, decrease in serum albumin.

Rare: Acute hepatitis.

Very rare: Hepatic failure.

Skin and subcutaneous tissue disorders

Common: Exanthema, erythema, pruritus.

Uncommon: Photosensitisation, loss of hair, increase in rheumatic nodules, skin ulcer, herpes zoster, vasculitis, herpetiform eruptions of the skin, urticaria.

Rare: Increased pigmentation, acne, petechiae, ecchymosis, allergic vasculitis.
Very rare: Stevens-Johnson syndrome, toxic epidermal necrolysis (Lyell's syndrome), increased pigmentary changes of the nails, acute paronychia, furunculosis, telangiectasia.

Musculoskeletal and connective tissue disorders

Uncommon: Arthralgia, myalgia, osteoporosis.

Rare: Stress fracture.

Not known: Osteonecrosis of jaw (secondary to lymphoproliferative disorders).

Renal and urinary disorders

Uncommon: Inflammation and ulceration of the urinary bladder, renal impairment, disturbed micturition.

Rare: Renal failure, oliguria, anuria, electrolyte disturbances.

Not known: Proteinuria.

Reproductive system and breast disorders

Uncommon: Inflammation and ulceration of the vagina.

Very rare: Loss of libido, impotence, gynaecomastia, oligospermia, impaired menstruation, vaginal discharge.

General disorders and administration site conditions

Rare: Fever, wound-healing impairment.

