3.5 SAMPLE SIZE CONSIDERATIONS

The primary efficacy endpoint is the rate of subjects meeting the ACR20. This response rate will be compared in subjects who received a given dose of ABX464 or placebo by likelihood ratio chi-square test. The result of the test will be interpreted in a descriptive manner therefore no adjustment for multiple comparison is applied.

For the sample size assessment, the following assumptions will be made:

- Response rate (ABX464): 0.65
- Response rate (placebo): 0.25

According to literature the ACR20 response rate for ABX464 + MTX treated subjects is expected to be between 50% and 65% while that in the placebo + MTX group is assumed to be approximately 25 to 30% (Xeljanz® Summary of Product Characteristics; ORAL Standard Investigators - N Engl J Med 2012; 367:508-519 August 9, 2012).

- Type I error: 10% two-sided
- Group allocation rate (ABX464 / placebo): 1:1:1

If the above assumptions and definitions hold true with a sample size of 60 subjects receiving two doses of ABX464 or placebo in a ratio of 1:1:1 the study has 84% power to show a difference in response rate between one active study group and placebo.

Subjects who terminates the study prematurely will be considered failures therefore no adjustment for drop-outs is needed.

Primary safety endpoint is the rate of all treatment emergent adverse experiences. The above sample size is sufficient to detect an increase in general treatment emergent adverse experience rate from 10% to 50% with 89% power by likelihood ratio chi-square test on a 10%, two-sided significance level.

If approximately 20 subjects receive ABX464 the study has 88% chance to detect at least 1 specific treatment emergent AE if the underlying rate of occurrence is 1:10. When the underlying rate of occurrence is around 1:20 the sample size of 40 subjects receiving active treatment is sufficient to observe at least 1 such an event with a probability of 87% in the active treatment group.

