3.6 RANDOMISATION

Eligible patients (i.e. those who fulfil all inclusion/exclusion criteria) will be randomized according to a 1:1:1 ratio into ABX464 100mg, ABX464 50mg or placebo treatment arms.

Up to 60 patients will be randomized in this study. At the beginning, the first 6 patients will be randomized to receive either ABX464 50mg (n=4) or its matching placebo (n=2). The Data Safety Monitoring Board (DSMB) will review the safety of these first 6 patients dosed for at least 2 weeks. Once the DSMB recommendation is granted, the next patients will be randomized to receive either ABX464 50mg, ABX464 100mg or placebo. Then, a second DSMB meeting will be held after the next 6 patients are randomized to check the tolerability of the 100mg dose. Once the DSMB recommendation is granted, the next patients will be randomized to receive either ABX464 50mg, ABX464 100mg or placebo.

Randomization will be performed via a centralized treatment allocation system that will be available 24 hours-a-day, 7 days-a-week. Randomization will be stratified according to previous exposure to anti-TNF α therapy. The bottle numbers to be used for a specific patient will be assigned according to a pre-defined randomization list.

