7 SAFETY MONITORING

An independent Data Safety Monitoring Board (DSMB), with expertise and experience in the pathology, and without direct involvement in the conduct of the trial, will be set up specifically to guarantee effective protection of patients, ensure the ethical conduct of the trial, benefit/risk ratio of the trial, and to ensure the independent review of the scientific results during the trial and at the end of the trial. Besides, the DSMB may recommend the early termination of the trial at any time if an unacceptable toxicity occurs.

The DSMB will meet after the first 6 patients are dosed (50mg or matching placebo) for at least 2 weeks to check the 50mg dose tolerability. Once the DSMB recommendation is granted, the next 6 patients will be randomized to receive either ABX464 50mg, ABX464 100mg or placebo. A second DSMB meeting will then be held when these 6 next patients are treated for at least 2 weeks, to check the 100mg dose tolerability and grant the recommendation to resume patient's randomization.

In addition, from the first DSMB onwards, meetings will be held every month during the study period. The DSMB will also review all potential causally-related Serious Adverse Events within 7 days of the initial report.

A dose limiting toxicity (DLT) is defined as a grade 3 or higher adverse event as defined by the Common Terminology Criteria for Adverse Events (CTC-AE V5.0) considered by a safety review board as probably or definitely related to study treatment. If more than 2 DLTs occur in the first 12 treated patients for at least 14 days, then the enrolment of additional patients in the treatment group will be stopped, otherwise the enrolment of planned patients will be confirmed. In addition, in case of a life threatening (grade 4) adverse reaction enrolment in the treatment group, all treatment of ongoing patients will be immediately discontinued. In both cases, enrolment will only be resumed upon the decision of the sponsor if the Data Safety Monitoring Board can conclude that the causality of the event was unrelated or unlikely related to study treatment.

The DSMB has only a consultative role. It will inform the Sponsor who will decide whether the DSMB recommendation will be followed. A DSMB charter must be available upon submission of the trial (initial protocol) to the respective competent authorities.

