Patient line plots will use actual time on the time axis. Mean plots will use a linear time scale for the nominal times of the visits and will be labelled by visit. Results from an early withdrawal visit will be excluded.

If changes in severity for the same TEAE have been reported separately but with the same AE number, they will be collapsed to a single AE with maximum severity for the summary tables, but listed as reported.

Classifications of medical history, concomitant medication and adverse events will be sorted alphabetically within the summary tables.

If any laboratory assessments are repeated at the same visit, the result from the repeat assessment will be used in summaries. Both values will be listed.

CRF data collected/ Data collected on the eCRF will be presented within data listings. The data listings will be sorted by treatment group, country, centre number, patient number and visit/week/day. Treatment group will be as allocated (randomised). If any patients receive the wrong treatment this will be flagged in all listings. Visits outside the visit windows will be identified within the listings. For patients who complete the study, the last visit will be described in the listings as '<Day X>'; for those who withdraw early it will be described as 'End of Study'.

The date format for all output presentations will be 'ddMMMyyyy'.

All statistical analysis will be performed using SAS 9.2 or higher.

All hypothesis testing will be carried out at the 5% (2-sided) significance level unless stated otherwise.

P-values will be rounded to four decimal places. P-values less than 0.0001 will be reported as <0.0001 in tables.

If any of the assumptions underlying the formal statistical methods proposed are violated during the analysis of the final data, alternative statistical methods will be used and any changes documented in the statistical methods section of the clinical study report (CSR), including the rationale for use.

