10.6 MULTIPLE COMPARISONS

There will be no corrections to nominal p-values for multiple comparisons because the results of the tests will be interpreted in a descriptive manner.

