11.6 SAFETY ANALYSES

11.6.1 Adverse Events

An overall summary table will be presented (any adverse event, any treatment emergent adverse event (TEAE), any serious adverse event (SAE), death, any grade 3 or higher adverse events from baseline to the end of Study) (*Table 14.3.1.1*). This analysis will be conducted on SAF population.

Primary safety endpoint, the rate of all treatment emergent adverse experiences, will be compared in subjects who received a given dose of ABX464 or placebo by likelihood ratio chi-square test on a 10% two-sided significance level (*14.3.1.2.1*).

Two periods will be defined for TEAE:

- Period I: any adverse event which occurs or worsens from first dosing to Day 84;
- Period II: any adverse event which occurs after Day 84.

Adverse events will be described by primary system organ class and preferred term according to the two periods. Numbers and percentage of patients, and number of occurrences of adverse event will be presented for:

- TEAE (Table 14.3.1.2.2 and Table Table 14.3.1.2.3);
- Serious TEAE (Table 14.3.1.3.1 and Table Table 14.3.1.3.2);
- TEAE leading to drug discontinuation (Table 14.3.1.4.1 and Table Table 14.3.1.4.2);
- TEAE of grade 3 or 4 (Table 14.3.1.5.1 and Table Table 14.3.1.5.2);

Further assessment of safety will be based on the frequency of adverse events (with and without regard to causality) graded according to the CTC-AE Classification and also, the review of individual values for clinical laboratory data, vital signs and ECG focusing on the detection of abnormal values and PCSAs [potentially clinically significant abnormalities (PCSAs) determined upon investigator considerations].

Adverse events will be tabulated (counts and percentages) by group. All adverse events will be listed, and the data will be tabulated by body system/organ class. Adverse event tabulations will include all treatment emergent adverse events, which will be further classified by severity, and relationship to treatment and dose level.

All adverse events (AE) will be classified using the version of the MedDRA coding dictionary specified in the DHM.

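### The likelihood-ratio chi-square for the primary TEAE comparison overshoots its 10% level if TEAEs are rare or near-universal in both arms, and the results shells carry one p-value for two dose-v-placebo comparisons (minor)

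*SAP*

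**What the plan says.** TEAE incidence is the primary variable (SAP 4.1). SAP 11.6.1 and protocol 8.4 both have it "compared in subjects who received a given dose of ABX464 or placebo by likelihood ratio chi-square test on a 10% two-sided significance level". SAP 3.5 and protocol 8.6 plan 60 patients at 1:1:1 and say this can detect a rise in the TEAE rate "from 10% to 50% with 89% power by likelihood ratio chi-square test on a 10%, two-sided significance level".

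Under SAP 3.6 the first six patients go four to 50 mg, two to placebo and none to 100 mg, with 1:1:1 allocation afterwards. Final arm counts after this start are not stated.

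Neither document has a rule for sparse tables. SAP 10.1 says only that, if assumptions prove to be violated, "alternative statistical methods will be used and any changes documented in the statistical methods section" of the study report. SAP 10.6 applies no multiplicity correction because "the results of the tests will be interpreted in a descriptive manner".

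In SAP section 15, the shells for Table 14.3.1.2.1 (TEAE) and Tables 14.2.1.1 to 14.2.1.3 (ACR20) show three arms and a single p-value. SAP 11.6.1 and 11.3.1 describe a comparison of a given dose with placebo.

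**The concern.** At a 10% rate, 20 patients give two expected events per arm. The likelihood-ratio statistic is poorly approximated by chi-square in such tables, and the error is towards too many rejections. The same happens in mirror image when nearly every patient has a TEAE. A p-value reported against a declared 10% level would then overstate the evidence of a difference.

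The single p-value cell is a separate matter. It could be filled with a three-arm test, which would not say which dose differs from placebo and would not be the comparison described in the text.

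**Working it through.** **Inputs.** Two-sided alpha 0.10 and the likelihood-ratio (LR) test (SAP 11.6.1); 20 per arm and rates of 10% and 50% (SAP 3.5). The first-six allocation (SAP 3.6) gives 18 (100 mg), 22 (50 mg) and 20 (placebo) if the remaining 54 patients split 18/18/18. That split is my assumption.

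**The plan's own power.** With p̄ the mean of the two rates, power = Φ{[|p1−p2|√n − 1.645√(2p̄(1−p̄))] / √(p1(1−p1)+p2(1−p2))}.

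- TEAE, 0.10 v 0.50, p̄ = 0.30: (1.789 − 1.066)/0.583 = 1.24, giving 89.2% (stated 89%).
- ACR20, 0.25 v 0.65, p̄ = 0.45: (1.789 − 1.157)/0.644 = 0.98, giving 83.7% (stated 84%).

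Both stated figures reproduce.

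**Exact size.** I enumerated every pair of event counts with both arms at the same rate and summed the probabilities of tables whose statistic exceeds 2.706, the 90% point of chi-square on 1 df.

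| Arms | LR size at 10% rate | of which harm direction (nominal 5%) | LR maximum, rates 20–80% | Low rates where LR size exceeds 12% (mirrored above 50%) | Pearson size at 10% rate | Pearson maximum, all rates |
|---|---|---|---|---|---|---|
| 20 v 20 | 17.3% | 8.6% | 11.7% | 2.8–15.6% | 10.3% | 10.7% |
| 18 v 20 | 13.9% | 7.7% | 11.9% | 5.5–18.9% | 9.5% | 10.5% |
| 22 v 20 | 13.8% | 6.4% | 11.1% | 4.9–16.1% | 9.8% | 10.0% |

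At 20 v 20 the LR size is 19.1% at a 5% rate, 12.4% at 15%, 10.6% at 20% and 9.5% at 50%. Its maximum is 20.2%, near 6.5%. At a 2% rate it falls to 8.0%. With 19 or 21 v 20, LR size at a 10% rate is 17.8% or 17.3%, and the Pearson maximum is 11.5% or 11.8%.

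**Where the excess comes from.** Take 2/20 v 0/20. Observed counts are 2, 18, 0, 20; expected are 1, 19, 1, 19.

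- LR: 2[2 ln 2 + 18 ln(18/19) + 20 ln(20/19)] = 2.88, p = 0.090, so it rejects.
- Pearson: 1 + 1/19 + 1 + 1/19 = 2.11, p = 0.147, so it does not.

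At a 10% rate this table, either way round, has probability 2 × 190 × 0.1² × 0.9³⁸ = 6.93%. The LR-minus-Pearson size difference is 17.28% − 10.34% = 6.94 points, so this one pair of tables accounts for essentially all of it.

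**Exact power, 10% v 50%** (20, 18 and 22 v 20). LR: 91.2%, 89.5%, 91.9%. Pearson: 90.7%, 89.5%, 91.8%. The largest loss is 0.5 points.

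**The single p-value.** As an illustration, suppose TEAEs occur in 8/20, 3/20 and 2/20 on 100 mg, 50 mg and placebo. A three-arm LR test gives p = 0.053. The pairwise LR tests give 0.024 for 100 mg v placebo and 0.63 for 50 mg v placebo.

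**The case against.** The strongest objection is that the affected range may never be reached. A reader might infer that the plan expects 10% of patients in both arms to have a TEAE, and hence that the primary test has a 17% false-positive rate. The documents do not support this: 10% is only the lower end of a detection scenario, and the size calculation needs both arms to sit there. Higher rates are plausible. The methotrexate product information in protocol Appendix 5 lists "Very common: Stomatitis, dyspepsia, nausea, loss of appetite, abdominal pain", and protocol section 7 says "Any disease progression will be reported in the eCRF both as an adverse event and documented in the efficacy section". A rate above 84% is possible too, but neither document gives a figure for it. This stands and limits the point to a conditional one.

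A reader might also infer that patients could be exposed to a wrong safety decision. That is not supported either. Action during the trial runs through the DSMB and the dose-limiting toxicity rule ("If more than 2 DLTs occur in the first 12 treated patients for at least 14 days"), neither of which uses this p-value, and the tests are read descriptively. This fixes the severity as minor but does not make the stated 10% correct.

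The fallback in SAP 10.1 is only a partial answer. It could cover sparse tables, but it names no method and acts only once the final data are being analysed.

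Finally, Pearson is also a large-sample test and does not hold exactly 10%. It reaches 11.8% at 21 v 20 and drops to 5.4% and 5.8% at a 5% rate with 19 and 21 v 20. That is fair, but its overshoot is much smaller than the likelihood-ratio test's. Fisher's exact test would overcorrect: at 20 v 20 its size at a 10% rate is 1.7% and its power 83.7%.

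On the shells, SAP section 15 allows layouts to change and the text should govern. Even so, the choice of comparison should not be left to programming.

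**Conclusion.** The point holds in conditional form and is minor. If both arms share a low or near-universal TEAE rate, the likelihood-ratio test does not hold its declared 10% level. Size exceeds 12% at common rates of about 3% to 16% or 84% to 97% with 20 v 20; at a common 10% rate it is 17.3%, or about 14% with 18 or 22 v 20. From 20% to 80% it is 9.5% to 11.9% for these three splits, and nothing material is wrong there.

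The figures assume independent patients, all dosed. The 18 and 22 arm sizes further assume that the first-six imbalance is not compensated. The stated 89% and 84% power figures are sound. The single p-value cell needs correcting whatever the TEAE rate turns out to be.

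**What to change.** Before unblinding:

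1. Name the uncorrected Pearson chi-square for the TEAE comparison in SAP 11.6.1 and in the footnote of the shell for Table 14.3.1.2.1. Across arms of 18 to 22 v 20 its size is at most 11.8% at any common rate.
2. Run it separately for 100 mg v placebo and 50 mg v placebo. Show two pairwise p-values in the shells for Tables 14.3.1.2.1 and 14.2.1.1 to 14.2.1.3, as SAP 11.6.1 and 11.3.1 already require.
3. In the TEAE power sentence of SAP 3.5, change the named test to Pearson and keep the 89%. List the departure from protocol 8.4 and 8.6 in SAP 1.2.

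Leave the ACR20 test and its 84% unchanged: at the assumed 25% placebo rate the likelihood-ratio size is 10.8%.

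The cost is a few lines of SAP text, one footnote and one extra p-value in two shell layouts. Sample size and data collection do not change. The downsides are that the TEAE and ACR20 comparisons then use different tests, and that TEAE power falls by less than 1 point.
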